#### **11.3.1 Datasets to be analysed, analysis populations**

All randomized subject will be included in the analyses

#### **11.3.2 Primary Analysis**

The primary analyses will be conducted at the end of the study by [name] [name], OBV (Chief of the EOC Biostatistic Service)

#### **11.3.3 Safety analysis**

The analysis of the safety will be conducted at the end of the study by [name] [name], OBV (Chief of the EOC Biostatistic Service). Parameters analysed will be the type and severity of AEs, treatment and resolution or stabilization (according to CTCAE Version 4.03 - June 14, 2010^12).

### **11.4 Handling of missing data and drop-outs**

In case of missing data, the patient will be dropped-out. 2 drop-outs each arm is planned

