
	
This procedure is usually a quite painful technique; thus, it is important to perform it after the spinal anaesthesia. It would be necessary to do it before the spinal anaesthesia just in case the pain would be associated to a nerve lesion. In this study the infiltration is not done on the nerve but in a muscular plane, thus is not needed the patient's sensibility.
 
The procedure will be performed at our institution by one of the three expert anaesthesiologists in the peripheral nerves' blockage. Those anaesthesiologists are:
 
 
• [name]. [name], Primario di Anestesia ORBV
 
• [name]. [name], Caposervizio Anestesia ORBV, board member of the Swiss Society of Loco-regional Anaesthesia
 
• [name]. [name], Caposervizio Anestesia e responsabile terapia del dolore ORBV
 

Control Intervention (if applicable):	None
Number of Participants with Rationale:	Based on previous studies we will expect a 33% reduction in VAS scale. To detect a clinically relevant difference between groups with a type I error of 0.05 and a power of 0.80 we determined a sample size of 18 subjects per group. Taken into account a possible drop out for different reasons of 10% we calculated the definitive sample size in 20 patients per group.
Study Duration:	According to the volume of the Milligan-Morgan hemorrhoidectomy performed every year in our centre, the estimated duration of the study is 2 years.
Study Schedule:	First-Participant-In planned: 01.01.2018 Last-Participant-Out planned: 31.12.2019
Investigator(s):	
[name] [name], Viceprimario Chirurgia ORBV, Bellinzona, [contact]
 
[name] [name], Caposervizio di Anestesia ORBV, Bellinzona, [contact]
 
[name] [name], Capoclinica Chirurgia ORBV, Bellinzona, [contact]
 
[name] [name], Medico Assistente Chirurgia ORBV, Bellinzona, [contact]

Study Centre(s):	Single-centre

[figure not shown]

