Statistical Considerations:	
Descriptive statistics will be presented as mean with standard deviation (SD) or as median with interquartile range (IQR) for quantitative data. Qualitative data will be presented as absolute numbers with percentages. Comparisons of postoperative pain measured on VAS scale at 6, 12 and 24 h after surgery between group A and group B will be performed with the non-parametric repeated measures analysis of variance (Friedman test). By statistically significant p-value, post-hoc tests will be performed taken into account the multiple comparisons. Qualitative data between groups of patients will be compared with the Chi-Square test, or the Fisher exact test as appropriate. By statistically significant result post-hoc comparisons were made with the appropriate critical level adjustment. Comparisons of quantitative data between groups will performed with the Student's t-test or with the Mann-Whitney test as appropriate. All tests will be conducted two-sided, and p-values < 0.05 will be considered statistically significant. Stata version 12.1 (StatCorp. LP, College Station, TX, USA) will be used for all statistical analysis.

GCP Statement:	
This study will be conducted in compliance with the protocol, the current version of the Declaration of Helsinki, the ICH-GCP or ISO EN 14155 (as far as applicable) as well as all national legal and regulatory requirements.
 
The Principal Investigator Dr. med [name] has obtained the GPC statement I and II level in June 2017

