## **5. STUDY OUTCOMES**

### **5.1 Primary Outcome**

Postoperative pain measured on VAS scale at 6, 12, 24, 48 hours

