### **9.2.4 Assessments in participants who prematurely stop the study**

Participants can be withdrawn from the study prematurely in case of adverse events after the pudendal nerve block.

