### **11.2 Determination of Sample Size**

Based on previous studies we will expect a 33% reduction in VAS scale. To detect a clinically relevant difference between groups with a type I error of 0.05 and a power of 0.80 we determined a sample size of 18 subjects per group. Taken into account a possible drop out for different reasons of 10% we calculated the definitive sample size in 20 patients per group.

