### **11.3 Planned Analyses**

Descriptive statistics will be presented as mean with standard deviation (SD) or as median with interquartile range (IQR) for quantitative data. Qualitative data will be presented as absolute numbers with percentages. Comparisons of postoperative pain measured on VAS scale at 6, 12 and 24 h after surgery between group A and group B will be performed with the non-parametric repeated measures analysis of variance (Friedman test). By statistically significant p-value, post-hoc tests will be performed taken into account the multiple comparisons. Qualitative data between groups of patients will be compared with the Chi-Square test, or the Fisher exact test as appropriate. By statistically significant result post-hoc comparisons were made with the appropriate critical level adjustment. Comparisons of quantitative data between groups will performed with the Student's t-test or with the Mann-Whitney test as appropriate. All tests will be conducted two-sided, and p-values < 0.05 will be considered statistically significant. Stata version 12.1 (StatCorp. LP, College Station, TX, USA) will be used for all statistical analysis.

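### Section 11.3.1 analyses every randomised patient, section 11.4 removes any patient with missing data, and nothing says which rule prevails or which missing item triggers removal

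*Combined protocol and SAP*

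**What the plan says.** Section 11.3.1 defines the analysis population in one sentence with no exception: "All randomized subject will be included in the analyses". Section 11.4 gives the only missing-data rule: "In case of missing data, the patient will be dropped-out. 2 drop-outs each arm is planned". Section 11.2, repeated in the synopsis, starts from 18 per group and adds an allowance: "Taken into account a possible drop out for different reasons of 10% we calculated the definitive sample size in 20 patients per group".

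Section 5.1 defines the primary outcome as "Postoperative pain measured on VAS scale at 6, 12, 24, 48 hours". The comparison in section 11.3 and the synopsis covers "VAS scale at 6, 12 and 24 h after surgery between group A and group B", using the Friedman test. Section 9.2.1 has VAS recorded by nursing staff or by the patient on a form.

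Section 8.4 covers data collection and follow-up for withdrawn participants but does not say whether their data are analysed. Sections 11.3.2 and 11.3.3 say who does the analyses, when, and which safety parameters are examined. No section names an imputation method, a sensitivity analysis, or an order of precedence between 11.3.1 and 11.4.

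**The concern.** A randomised patient with one blank VAS reading is in the analysis under 11.3.1 and out under 11.4. Both are operative rules in the statistical section, so the primary analysis population is not fixed once anything is missing. If this stays open, the choice could be made after outcomes are known.

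The trigger is undefined too. A patient missing only the 48-hour score has incomplete primary-outcome data under 5.1 but complete data for the test in 11.3. The wording of 11.4 could even reach a blank item that has nothing to do with pain.

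Applied literally, 11.4 also throws away the scores that the removed patient did provide. The patients who remain are selected after randomisation, so randomisation no longer protects the comparison. Because some forms are self-completed, an occasional blank is plausible.

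**Working it through.** **The rules side by side.** For a patient with complete data, 11.3.1 and 11.4 agree. For any other patient they give opposite answers. With the planned two losses per arm, 11.3.1 gives 40 analysed and 11.4 gives 36, a difference of 4 patients or 10% of the trial.

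**Inputs from the plan.** Two-sided 0.05 (11.2, 11.3); power 0.80, 18 per arm needed, 10% drop-out, 20 per arm enrolled (11.2); k = 4 VAS times (5.1) or 3 (11.3).

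**Assumptions.** The plan gives no SD, control mean or missing-data rate. I use a two-sample t-test on one normal outcome, not the planned Friedman test, and a missing probability per reading, m, of 1% or 5%.

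1. *The plan's own figure.* 18 / (1 − 0.10) = 20 per arm, and 20 × 0.10 = 2 drop-outs, leaving 18. Sections 11.2 and 11.4 agree arithmetically.

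2. *Implied effect.* Solving the t-test for n = 18 per arm and power 0.80 gives a difference of 0.961 SD. At that difference, power is 0.842 with 20 per arm and 0.800 with 18.

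3. *How often the rules clash.* With independent missingness, the chance of no missing reading in 40 patients is (1 − m)^(40k). At m = 0.01 this is 0.99^120 = 0.30 or 0.99^160 = 0.20. With missingness correlated 0.5 within patient (beta-binomial), it is 0.48 or 0.43. Even at 1% per reading, a clash is more likely than not.

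4. *What 11.4 costs if readings go missing independently.* Patient loss is 1 − (1 − m)^k, and the share of recorded values discarded is 1 − (1 − m)^(k−1). At m = 0.05:
   - k = 3: loss 1 − 0.95^3 = 0.143; 17.1 per arm remain; power 0.78; 9.8% of recorded values discarded.
   - k = 4: loss 1 − 0.95^4 = 0.185; 16.3 per arm remain; power 0.76; 14.3% discarded.
   - The 10% allowance is used up at m = 1 − 0.9^(1/3) = 3.5% or m = 1 − 0.9^(1/4) = 2.6%.

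5. *The same with within-patient correlation 0.5.* The chance that a patient is complete is 0.95 × (1.95/2) × (2.95/3) = 0.911 for k = 3; multiplying by 3.95/4 gives 0.899 for k = 4. Loss is 0.089 or 0.101 and power 0.805 or 0.800, the planned level. The share of recorded values discarded is 4.1% or 5.3%.

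6. *Using every recorded value.* Take the mean over times, correlation 0.5 between a patient's VAS scores, and independent missingness at m = 0.05. A patient with j readings contributes information proportional to j / (1 + 0.5(j − 1)). Averaged over j, this gives an effective 19.65 (k = 3) or 19.74 (k = 4) per arm and power of about 0.84.

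**The case against.** **The sections can be reconciled.** Section 11.3.1 may be the general rule and 11.4 the specific exception. The Friedman test needs complete blocks, so 11.4 may simply follow from it, and one named analyst will apply it. This is plausible, but no text says so. If it is the intention, the statement in 11.3.1 is untrue as written, the trigger stays undefined, and recorded scores are still discarded.

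**The inflation in 11.2 is ordinary.** A reader might infer that enrolling 20 to retain 18 itself contradicts 11.3.1. It does not. An allowance for loss is compatible with analysing everyone randomised; it shows only that the planned power tolerates two losses per arm. The conflict lies in the removal instruction in 11.4.

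**The power effect is small.** This stands. A reader might infer a seriously underpowered trial, but the illustration shows at most a few points below 0.80, and none with within-patient correlation 0.5. The figures also assume the 20 per arm of 11.2, whereas section 6.1 states 100 patients. At 50 per arm and the same 0.961 SD, power would be about 0.99 even after the losses in step 4. The clash would then be more frequent: at 1% per reading and independent missingness, the chance of no missing reading falls to 0.99^300 = 0.05 or 0.99^400 = 0.02.

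**Withdrawal for adverse events.** Section 9.2.4 says "Participants can be withdrawn from the study prematurely in case of adverse events after the pudendal nerve block". Group B has no block (8.2.2), so this ground can arise only in group A, and a reader might infer material bias. The documents do not support that: the wording is permissive, and section 2.2 calls the block's risks extremely rare. In simulated null trials where the highest-pain group A patients were always the ones removed, type I error was about 5.2% or 5.4% at assumed event rates of 0.5% or 1%. It reached 7.5% only at 5%. This is a minor note.

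**Conclusion.** The plan is wrong as written: two stated rules for who is analysed conflict, no section ranks them, and the missing item that triggers removal is not defined. This conclusion comes from the text and needs no numerical assumption. On the plan's own allowance the rules differ by 4 of 40 patients.

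The consequence is mainly for the validity and pre-specification of the primary comparison. Power differs by about 4 points between 20 and 18 per arm analysed (0.84 against 0.80). It falls to about 0.76–0.78 only under the assumed 5% independent missingness. These sizes rest on a back-solved effect, a t-test and 20 per arm. They do not show that the trial is underpowered or that its result would be biased in a known direction.

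**What to change.** Replace the removal rule in 11.4 with: *All randomised patients with valid consent are analysed in their allocated group using every recorded VAS value. Patients with no VAS value are counted by arm. A complete-case analysis is a sensitivity analysis.* Then:

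- Name one list of VAS times, identical in 5.1, 11.3 and the synopsis, before any data are seen.
- In 11.3 and the synopsis, replace the Friedman test with one pre-specified between-group repeated-measures method that accepts incomplete readings, and state that it assumes missing at random. A linear mixed model with group, time and group-by-time, a small-sample correction and one named contrast is a workable choice, not the only one.
- Keep the 10% and the two drop-outs per arm only as a sample-size allowance, and reconcile the 40 patients of 11.2 with the 100 of 6.1.
- State in 8.4 that VAS data collected after withdrawal from treatment are kept and analysed unless consent is withdrawn. Report withdrawals by arm with reasons. Clinical withdrawal criteria stay with the investigators.

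The cost is an amendment approved by the ethics committee, slightly more analysis work, and reliance on a model and its missing-at-random assumption. The analysis change itself needs no extra patients, visits or forms.

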## **12. QUALITY ASSURANCE AND CONTROL**

The Principal investigator is responsible for maintaining quality assurance and quality control, he is also responsible for proper training of all involved study personnel.

### **12.1 Data handling and record keeping / archiving**

All the data will be collected on specific printed Case report form for each patient. The Principal Investigator will preserve the sensitive data in his office in a closed cabinet key.

#### **12.1.1 Case Report Forms**

A paper Case Report Forms will be used. Participants will not be identified in the CRF by name or initials and birth date. Appropriate coded identification will be used and managed by the Principal Investigator.

The Principal Investigator, Coordinators, data collector, authorised representatives of the Sponsor (-Investigator), the monitor, a competent authority or an ethics committee may have direct access to parts of the medical records relevant to the study. They are authorized to CRF access.

Results will be then collected on a Redcap® electronic database. The access to the database will require username and password. Only the authorized personnel (physicians responsible for the study) will have the access rights and all changes on the database are trackable.

#### **12.1.2 Specification of source documents**

Source data on the CRF include the original documents relating to the study, as well as the medical treatment and medical history of the participant (demographic data, clinical data, participation in study and Informed Consent, VAS scale at 6, 12, 24, 48, drugs taken, length of hospital stay, complications).

#### **12.1.3 Record keeping / archiving**

The Principal Investigator will preserve the sensitive data in his office in a closed cabinet key, archiving for 10 years. The e-database Redcap® grants security standard according to the EOC sensible data system storage and security.

## **12.2 Data management**

The Principal Investigator has the overall responsibility for the data management.

### **12.2.1 Data Management System**

CRF paper will be used and secured by the principal investigator in his office in a closed cabinet key. Results will be then collected on a Redcap® electronic database. The access to the database will require username and password. Only the authorized personnel (physicians responsible for the study) will have the access rights and all changes on the database are trackable (double data entry).

### **12.2.2 Data security, access and back-up**

CRF paper will be used and secured by the principal investigator in his office in a closed cabinet key. Results will be then collected on a Redcap® electronic database. The access to the database will require username and password. Only the authorized personnel (physicians

responsible for the study) will have the access rights and all changes on the database are trackable (double data entry).

CRFs and the electronic database will be accessible only by authorized personnel (physicians responsible for the study). Authorised representatives of the Sponsor/Investigator, the monitor, a competent authority or an ethics committee will have the access to sensible data.

### **12.2.3 Analysis and archiving**

Results will be then collected on a Redcap® electronic database. The access to the database will require username and password. Only the authorized personnel (physicians responsible for the study) will have the access rights and all changes on the database are trackable. Sensitive data will be archived for 10 years.

## **12.4 Audits and Inspections**

The monitor will perform 2 inspections / year and will send to the Local Ethical Committee 1 report / year about safety data.

## **12.5 Confidentiality, Data Protection**

The Principal Investigator has the overall responsibility for the data management. Data will be accessible only by authorized personnel (physicians responsible for the study). Authorised representatives of the Sponsor/Investigator, the monitor, a competent authority or an ethics committee may have direct access to parts of the medical records relevant to the study. They are authorized to CRF access.

## **13. PUBLICATION AND DISSEMINATION POLICY**

The trial results will be communicated to the healthcare professionals, the public and other relevant groups via publication

**14. FUNDING AND SUPPORT**

None

**14.1 Funding**

None

**14.2 Other Support**

None.

**15. INSURANCE**

Not needed

## 17. APPENDICES

Other documents needed are listed:

1. Informed consent
2. Patient's formulary (CRF include all the clinical information to be collected in the trial)
3. Protocollo per pazienti ambulant
